3.1.6 Stent-graft deployment

The procedure will be performed in the operating room under local, epidural or general anesthesia depending on patient factors. The patient will be positioned on a radiolucent operating table to permit fluoroscopic examination of the entire abdomen and groins. A high-resolution digital imaging system is required to guide placement. Other desirable imaging features include last image hold, digital subtraction, roadmapping, and hard copy output. Grafts may be inserted from either femoral artery with consideration given to the degree of tortuosity and occlusive disease noted from preoperative imaging techniques. The lower chest, abdomen and groins are prepared and draped in the usual sterile fashion. One common femoral artery is exposed and dissected free from surrounding structures using standard surgical techniques. A soft, relatively disease free portion of the anterior common femoral artery is selected for an arteriotomy. Double-looped tapes or vessel loops are used to encircle the common femoral or distal external iliac artery proximal and distal to the proposed site for arteriotomy. If the common femoral artery and external iliac arteries are too diseased to permit hemostasis using vascular loops, a short graft may be anastomosed to the femoral artery to serve as a conduit to the proximal arterial tree. Heparin is administered (100-150 units/kg) by intravenous injection 3 minutes prior to occlusion of the femoral artery. The loops are tightened to provide proximal hemostasis.

An angiographic catheter is passed through the femoral arteriotomy into the proximal aorta. An angiogram is performed. Using the angiogram as a reference, the limits of the proximal and distal cuffs are marked on the patient with a radio-opaque marker. Alternatively, the angiogram can be stored as a roadmap, to be superimposed on subsequent fluoroscopic images. Correct positioning of the prosthesis depends on the relationship of the imaging system to the patient. The angiographic catheter is then exchanged over a stiff guidewire for the delivery system. The system is advanced to bring the metal stents to the desired location. The position of the graft, as indicated by the position of the proximal and distal stents, can be maintained during extrusion by manipulation of the carrier. Assuming a bifurcated system is used, the femoral artery on the contralateral leg is then exposed. A steerable catheter and guidewire combination is used to cannulate the contralateral limb from within the aneurysm sac. The position of the catheter within the stent-graft is confirmed angiographically. Following complete deployment of the main stent-graft body, the contralateral limb is deployed over a stiff guidewire.

Withdrawing the sheath slowly over the carrier extrudes the main stent-graft and the contralateral limbs. It is easier to maintain the correct position of the graft if the hand controlling the carrier is braced upon the patient's leg. Throughout the procedure, angiographic evaluation can be intermittently assessed using the delivery sheath to administer contrast agent. Hemostasis is maintained by tension on the proximal loops, which compresses the common femoral arterial wall against the delivery system. Following graft deployment, the delivery system is removed through the femoral arteriotomy. Aortography is then performed with the intent of visualizing exclusion of the aneurysm sac. The presence of contrast material in the aneurysm sac is indicative of an endoleak, which may be treated at that time by modifications of the proximal or distal fixation points. Appendix D contains a more detailed and diagrammatic description of the procedure.

3.1.7 Perioperative Care

The endovascular method calls for no departure from the usual perioperative management of patients undergoing aneurysm repair. The preoperative evaluation and intraoperative monitoring will be performed as though the patient was undergoing conventional repair. Post-operative management will be dictated by clinical circumstances, and is likely to differ somewhat from the usual management of patients following aneurysm repair, because the patients tend to experience fewer physiologic derangements.

3.2.2 Preoperative Assessment Data Points

Patients meeting the selection criteria who have provided informed consent will undergo a detailed preprocedural examination. Data will be collected and stored in a database. This database is constructed with the intent of capturing both study specific data, and information that will prove useful to our clinical practice, and research regarding the general subject of the endovascular management of aortic disease. Data collection will be simplified such that one basic form will obtain the majority of the necessary data for research, development, as well as compliance with both institutional and national study specific requirements. The sections that will not be viewed as study specific are shaded grey. Please refer to Appendix E for more detail. Data points include:

- 1) date of examination
- 2) date of hospital admission
- 3) age, sex, weight, and height
- 4) risk factors including:
 - a) smoking
 - b) diabetes
 - c) hypertension
 - d) cardiac disease
 - e) renal disease
 - f) pulmonary disease
- 5) prior peripheral vascular procedures
- 6) lower extremity pulse assessment or Doppler and ABI evaluation
- 7) radiographic results
 - a) proximal neck length, diameter, angulation
 - b) distal neck length, diameter, angulation
 - c) length of infrarenal aorta to be grafted
 - d) common iliac artery measurements
 - e) extent of visceral artery occlusive disease
- 8) baseline laboratory data

3.2.3 Intraoperative Data Points

The endovascular aneurysm procedure will be documented in such a way to permit analysis of any untoward occurrences in terms of cause and effect. Data will be collected and stored in a database. Data points include:

- 1) date of procedure
- 2) procedure time (skin to skin)
- 3) endoprosthesis time (from insertion of initial catheter to removal of the inner catheter of the delivery system)
- 4) contrast medium type and total volume infused
- 5) estimated blood loss
- 6) total amount of blood transfused and cell saver transfused
- 7) diameter, length and configuration of the prosthesis
- 8) assessment of system performance addressing: ease of insertion, accuracy of placement, ease of removal
- 9) ancillary equipment needed

- 10) adjunctive maneuvers including: balloon dilation of iliac arteries, additional stents required, additional surgical procedures, maneuvers to move or re-align stents, the need for thrombectomy
- 11) nature of completion assessment
- 12) findings of completion assessment: endoleak, kinks, twists, angulation of stents

3.2.4 Postoperative Course Data Points

The interval between deployment of the endoprosthesis and discharge from the hospital will be documented. Data points include:

- 1) date of discharge
- 2) survival or death – if the patient has died, a death form should be filled out
- 3) complications (if any)
- 4) patient withdrawal from study
- 5) postoperative imaging information: CT scan, KUB are mandatory
- 6) time to resumption of regular diet
- 7) time to first bowel movement
- 8) time to resumption of normal mobility
- 9) maximum daily temperature up to time of discharge or day 14
- 10) peripheral vascular exam at time of discharge including pulses or an ABI
- 11) blood tests at time of discharge (CBC, BUN, Cr)

3.2.5 Follow-up

The results of the endovascular repair will be assessed by radiologic and/or clinical criteria at the time of graft insertion, prior to hospital discharge, between two and four weeks at a follow-up appointment, and according to the postoperative imaging schedule listed below.

	Pre-op	Intra-op	Prior to d/c	1 month	6 month	12 months	24 month
CT Scan	X*		X	X	X	X	X
Angiography	X	X					
KUB			X	X	X	X	X

A series of blood tests including blood urea nitrogen, complete blood count, and creatinine will be obtained on the same schedule as the CT scans. Additional data points to be obtained during follow-up include:

- 1) date of follow-up
- 2) survival or death
- 3) complications (if any)
- 4) patient withdrawal
- 5) findings of any imaging abnormalities
- 6) peripheral vascular exam or ABI
- 7) blood test (CBC, BUN, Cr)

3.2.6 Adverse Events

3.2.6.1 Deaths

Details of any deaths occurring during the evaluation will be stored in a database. Data points include:

- 1) immediate cause of death
- 2) underlying cause of the fatal condition
 - a) related to the prosthesis
 - b) related to the procedure
 - c) related to a previous condition
- 3) status of the prosthesis at the time of death

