We only consider endovascular repair a failure if the aneurysm ruptures, or the patient dies in the perioperative period (30 days), undergoes open surgical repair, or has signs of endoleak on contrast-enhanced CT. This definition of overall success includes the patients in whom repair was always successful (continuing success), and those in whom an endoleak resolved or was treated by endovascular means (secondary success), as described in the SVS/ISCVS Reporting Standards for Infrarenal Endovascular Abdominal Aortic Aneurysm Repair.⁹

EUROPEAN EXPERIENCE WITH BIFURCATED STENT GRAFTS

By these criteria, endovascular aneurysm repair was considered successful in 50% of the first 20 cases performed with bifurcated grafts, 75% of the next 20, and 100% of the last 17. The most common cause of failure was graft thrombosis in the first group and stent-graft migration in the second group. The technical modifications responsible for the elimination of these complications are described among the general comments on technique previously listed. Another factor in the high success rate achieved in the last group may have been the inclusion of results with the industry-made device. The thin-walled graft used in the industrial device proved to have significant advantages.

SAN FRANCISCO EXPERIENCE WITH STRAIGHT AORTO-AORTIC AND TAPERED AORTO-UNILIAC STENTGRAFTS

Eighty high-risk patients with large aneurysms have been assessed by CT and catheter angiography since this program's inception in July 1996. Endovascular repair was thought to be feasible in 54 (70%). Forty-six of these have been treated electively, and another 4 on an urgent basis. The results in the 46 cases of elective endovascular aneurysm repair were as follows. There were no deaths and no conversions to open operation. The operating time was 190 ± 71 min (mean \pm standard deviation), estimated blood loss was 303 ± 402 ml, and contrast volume was 153 ± 70 ml. The time from operation to resumption of a normal diet was 0.58 ± 0.58 days, to ambulation was 1.17 ± 0.8 days, and to discharge was 3.42 ± 1.51 days. Most of the complications were related to the open surgical aspects of the case. Hematoma requiring reoperation occurred in 3 patients, seroma in 1, wound necrosis in 3, and wound infection in 2. One patient suffered a non-Q-wave MI without significant sequelae. Another patient had self-limited signs of digital embolism.

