Once the catheters are in place, the right femoral artery is opened and the delivery system introduced over the guidewire. Proximal stent deployment is guided by angiographic localization of the renal arteries using the left sided angiographic catheter to inject contrast. Sheath withdrawal exposes the left-limb catheter at the groin. The cross-femoral catheter is used to tow the left-limb catheter from the right femoral artery to the left. Further traction pulls the left limb of the graft into the left common iliac artery (Figure 1). The small sheaths are then removed, allowing the distal stents to deploy. The procedure is completed by bilateral Wallstent insertion. Both graft limbs are completely stent supported.

Follow-Up

The exact protocol varied from center to center, but all cases were examined by computed tomography scan prior to discharge from the hospital. Computed tomography was repeated at 6, 12, 24 and 48 months. In addition, some centers performed computed tomography at 3 and 18 months, and some performed routine angiography as part of the follow-up.

Results

The patients are allocated groups 1, 2, and 3, depending on when the insertion procedure was performed. Group 1 includes the first 20 patients, group 2 the next 20, and group 3 the most recent 17. Complications related to the function of the stent-graft are listed in Table 1. Complications of a more general nature are listed in Table 2.

Stent-graft insertion is considered to have failed if the patient dies, the stent-graft has to be removed, or there is perigraft flow on contrast-enhanced computed tomography. These causes of failure are listed in Table 3.

Table 1 Stent-graft-related complications

Complication	Group 1 (n = 20)	Group 2 (n = 20)	Group 3 (n = 17)
Failed insertion	2	1	0
Thrombosis	6	0	0
Aneurysm rupture	1	1	0
Migration	1	4	1
Graft infection	1	0	0

Table 2 Other complications

Complication	Group 1 (n = 20)	Group 2 (n = 20)	Group 3 (n = 17)
Renal failure	1	1	0
Myocardial infarction	1	1	0
Wound infection	1	0	0
Hematoma	0	1	0

Table 3 Criteria of success

Criterion	Group 1 (n = 20)	Group 2 (n = 20)	Group 3 (n = 17)
Initial leak	4	2	1
Current leak	0	1	0
Explant or death	9	5	0
Success	11(55%)	14(70%)	17(100%)

Discussion

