them have been bifurcated grafts for infrarenal aorto-iliac aneurysmal disease. All the grafts were made in one institution and had similar components. Median follow-up period is 18 months (range 1 to 36 mo.). For the bifurcated system, the operating time and blood loss reduced with experience and improvement in the technique and delivery system (Table 2). Primary success, defined as a technically successfully deployed graft in the correct position and with no occlusion or evidence of endoleak at the time of discharge from hospital, was achieved in 94 cases, giving a primary success rate of 87%. Of the 14 failures, there were 2 deaths: 1 postoperatively and 1 at day 7. There were 3 cases where the graft could not be completely deployed and 9 endoleaks. There were a total of 15 endoleak by 6-week follow-up; the 9 noted initially, 3 associated with failure to deploy, and a further 3 late endoleaks. Of these, 7 were treated by a secondary endovascular technique and 4 sealed spontaneously. Two patients have died of unknown causes but with a persisting endoleak, and 2 small distal leaks persist and are being observed. None of the grafts have occluded, but there have been 3 cases of occlusion of a limb of the graft. One of these was successfully treated with a Palmaz stent, and the other 2 persist untreated. There have been no cases of intraprocedural rupture of an aneurysm. There have been

Table 2. Patient Demographics

Number	108
M:F	91:17
Age (median)	78
(range)	52-89
Size of AAA (cms)	5.5(4.5-10)
Myocardial infarction (%)	22
Angina (%)	32
CABG (%)	10
COAD (%)	23
Diabetic	10
Hypertension (%)	56
CVA (%)	6
Peptic ulcer (%)	22
Renal failure (%)	12

cases of conversion to an open aneurysm repair. One of these was an early conversion and resulted in patient death. Two cases of late conversion to open repair are currently alive.

Ninety-one patients are currently alive. Of the 17 deaths, 12 were of unrelated causes. There were 2 early deaths, and 2 patients who died of unknown causes with a persisting endoleak. One patient died of mesenteric vascular insufficiency attributed to the procedure.

Taking into account the 11 endoleaks that sealed following a secondary procedure or spontaneously, the 5 deaths related to the procedure, the 2 persisting endoleaks, and the 2 persisting limb occlusions, the overall secondary success rate is 90% (97/108).

COMPLICATIONS

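### Does the plan need a rule, fixed in advance, for which deaths count as failure of the repair?

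*Combined protocol and SAP*

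**What the plan says.** Objective 1 (section 1.1.0) is safety and efficacy in preventing aneurysm growth and rupture. Section 3.1.0 describes a prospective, non-randomized evaluation, and section 2.0 sets 300 high-risk patients without a calculation.

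For each death, section 3.2.6.1 records the immediate cause, the "underlying cause of the fatal condition" and the state of the prosthesis when the patient died. The underlying cause has three options: the prosthesis, the procedure, or "related to a previous condition". Section 3.2.6.2 asks for autopsy in every patient who dies with a prosthesis in place. Section 4.3.3, which is risk/benefit background, regards a patient free of endoleak as effectively treated and one with an endoleak as unfinished business. It does not mention deaths.

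The appended papers each use their own rule:
- Appendix G: "Stent-graft insertion is considered to have failed if the patient dies, the stent-graft has to be removed, or there is perigraft flow" on CT. No time or cause limit is put on death.
- Appendix F: failure is rupture, or "the patient dies in the perioperative period (30 days), undergoes open surgical repair, or has signs of endoleak on contrast-enhanced CT".
- Appendix H: secondary success takes account of "the 5 deaths related to the procedure", persisting endoleaks and persisting limb occlusions.

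The plan adopts none of these. What stands between sections 3.1.7 and 3.2.2, what stands between section 5.2.0 and the reference list, and the contents of the Appendix E form were not available to this review, so absence can be claimed only for the rest.

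**The concern.** Patients enter because their anticipated mortality with open surgery exceeds 10 percent, so deaths from other disease are to be expected. In Perth they were 12 of 17 deaths (71%). If one success percentage is reported, the treatment of those deaths could move it more than all the other failures together. A rule chosen after the data are seen could flatter the device, and a comparison with Perth would not be like for like unless the same rule were used. Unexplained deaths with an open endoleak are the awkward cases: section 3.2.6.1 lists no option for an unknown cause, and autopsy can be requested but not guaranteed.

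**Working it through.** **Inputs (Appendix H, Results).** 108 patients, 91 alive. "Of the 17 deaths, 12 were of unrelated causes"; the others were 2 early, 2 of unknown cause with a persisting leak, and 1 from mesenteric insufficiency. Non-fatal failures: 2 leaks under observation and 2 late conversions ("Two cases of late conversion to open repair are currently alive").

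**Reproducing the printed figures.**
- Deaths: 12 + 2 + 2 + 1 = 17 = 108 − 91.
- Primary success: 108 − (2 + 3 + 9) = 94; 94/108 = 87.0%, as printed.
- Secondary success: the listed deductions 5 + 2 + 2 = 9 give 99. Also deducting the 2 late conversions gives 108 − 11 = 97; 97/108 = 89.8%, the printed 90%.
- The 5 procedure-related deaths are reached only as 2 early + 1 mesenteric + 2 unknown.

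**Changing only the death rule.** Success = (108 − failures)/108, with the 4 non-fatal failures fixed and limb occlusions left out, since Appendices F and G do not count them. Exact 95% intervals in brackets.

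| Rule | Failures | Success |
|---|---|---|
| Any death (Appendix G) | 17 + 4 = 21 | 87/108 = 80.6% (71.8–87.5) |
| Procedure-related deaths (Appendix H count) | 5 + 4 = 9 | 99/108 = 91.7% (84.8–96.1) |
| 30-day death, or dead with open leak (Appendix F) | 2 + 2 + 4 = 8 | 100/108 = 92.6% (85.9–96.7) |

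The spread is 13/108 = 12.0 points: the 12 unrelated deaths (11.1) plus the mesenteric death (0.9). Deducting the 2 limb occlusions throughout gives 78.7%, 89.8% and 90.7%, with the same spread.

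**Sensitivity to the assumptions.**
- Mesenteric death within 30 days: the Appendix F result becomes 99/108 = 91.7%.
- The 2 patients who died with a leak not counted: 102/108 = 94.4%.
- Late conversion not treated as graft removal: the Appendix G result becomes 89/108 = 82.4%.

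A fair range is therefore 80.6–82.4% at the low end and 91.7–94.4% at the high end.

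**A check inside the documents.** Appendices F and G appear to report the same bifurcated cases in groups of 20, 20 and 17.
- Appendix F: 0.50 × 20 + 0.75 × 20 + 1.00 × 17 = 10 + 15 + 17 = 42.
- Appendix G, Table 3: 11 + 14 + 17 = 42.

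Both give 42/57 = 73.7%. Groups 1 and 2 differ by one patient each, in opposite directions. In group 1 the narrower death rule gives the lower success rate, so the death rule alone does not explain that difference.

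**Can the trial's data support either reading?** Procedure date (3.2.3), survival status and imaging findings at each visit (3.2.5), date of and reason for explant (3.2.6.2), and cause of death with prosthesis status (3.2.6.1) are all collected. The lists do not name a date of death; I assume the death form carries one. With that, each of the three rules can be applied to the trial's own patients.

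**The case for a change.** The strongest case for a change is that 12.0 points exceeds sampling error: at n = 300 the 95% half-width, 1.96 × √(p(1 − p)/300), is 4.5 points at p = 0.806 and 3.0 at p = 0.926. Nor is there one obvious default, since the plan's own appendices disagree. The Background already shows how a cause can drift: it says two Perth patients with endoleak died of unrelated causes, where Appendix H says the causes were unknown and needs those deaths to reach its 5. A short paragraph of rules would cost little.

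The missing rule, the arithmetic and the slip all stand. The inference that the plan must change does not. The 12 points measure the distance between two different quantities, survival free of failure and failure of the repair itself; they are not uncertainty about what happened to patients. A descriptive report can give both. The Background's overall tally (12 unrelated, 2 unknown) agrees with Appendix H, so the sentence is a clerical error and not a counting rule. A competing-event analysis with unexplained deaths counted as failures would be reasonable, but it is one choice among several, replaces no stated method, and would still leave non-fatal failure undefined.

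**Conclusion.** No change to the plan follows. This is a gap that analysts can fill sensibly. Nothing in the study turns on a single success rate: no success percentage, threshold, test or comparison is stated. The data collected allow all-cause survival, early mortality and cause-specific failure to be shown together, with unexplained deaths visible. Whether an unknown-cause code exists is a detail of the unseen form that staff would supply.

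The illustrative size is about 12 points in the Perth patients (80.6% to 92.6%, with the ends moving to 82.4% and to 91.7–94.4% under other readings). It assumes that late conversion means graft removal, that the fatal early conversion is among the deaths already counted, that the non-fatal failures are distinct living patients, and that the mesenteric death came after 30 days. The conclusion would need another look if the study were to be judged on one success percentage against a target or an earlier series.

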3.2.6.2 Explants

Autopsy will be requested in all patients who die with a prosthesis in place. At the autopsy, the entire abdominal aorta will be excised – from the celiac axis down to and including both common iliac arteries. The specimen will undergo histologic examination.

When the prosthesis is excised in the course of conversion to open repair, the position, and attachment of the prosthesis within the arterial tree will be recorded. In addition, every care will be taken to ensure that the prosthesis is removed intact. For example, vascular clamps will be applied at remote sites from stent attachments. The prosthesis will then be washed with saline to remove surface thrombus. The graft components will be fixed in 4% formaldehyde for subsequent histologic examination. Data will be collected and stored in a database. Data points include:

- 1) date of explant
- 2) patient's status at explant
- 3) reason for explant
- 4) degree of attachment / ingrowth

